	
educational course and completing self-reported questionnaires and possibly two semi-structured qualitative interviews.
 
Any potentially psychological risks from participating in the study have been addressed by contingency plans to provide links to Online help resources and the contact details of study team members to provide further information for participants.

Statistical Methods:	
Analysis of outcomes:
 
Characteristics of quality of life (QoL) will be measured by the MSQOL-54, including physical and mental health composite scores and multiple subdomains. Linear regression will be used to determine cross-sectional and prospective relationships with QoL. Characteristics of disability will be assessed using linear regression. Characteristics of dichotomous clinically significant fatigue and depression will be assessed by log-binomial regression. Characteristics of self-efficacy composite scores will be assessed by linear and log-binomial regression for continuous and dichotomised self-efficacy, respectively. All models will be assessed for potential clinical and demographic confounders and appropriate adjustments will be made in analyses.

Subgroups:	Not applicable
Consumer Involvement	
Consumers have been involved in the co-design of the MSOC RCT. A consumer advisory group comprising of 6-8 people with MS in a series of focus groups was involved in the co-design of the MS Online intervention and standard-care course. The devised course was then tested in a feasibility study (MSOC – Feasibility) involving a subgroup of people with MS (n = 31) and the quantitative and qualitative outcomes of the MSOC – Feasibility study were used to co-design the MS Online intervention and standard-care courses in the proposed RCT.

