The 12-item multidimensional Scale of Perceived Social Support (MSPSS) will be used to measure participants' social interaction and satisfaction with social support (Zimet, Dahlem, Zimet, & Farley, 1988). Higher score of MSPSS indicates higher quality of social support.

Health outcomes of participants will be assessed at baseline and 6, 12 and 30 months after completion of the respective Online MS course. Health outcomes measured include:

f. Mental and physical quality of life (qol)

The MSQOL-54 will be used to assess a spectrum of HRQOL outcomes. In particular, the two primary outcome measures for this study will be change in Physical Health Composite (PHC) and Mental Health Composite (MHC) derived from the MSQOL-54. PHC and MHC are derived by combining scores of relevant subscales (Vickrey, Hays, Harooni, Myers, & Ellison, 1995). Although minimal clinically important differences have not been established for the MSQOL-54 composite scores, differences of at least five points have previously been determined as the minimum clinically meaningful change in an HRQOL measure (Osoba et al., 1998; Taphoorn, et al., 2005). This is based on recommendations that a difference

equivalent to half the standard deviation be universally considered an important magnitude for all HRQOL tools (Norman, Sloan, & Wyrwich, 2003). The MSQOL-54 has been psychometrically validated since 1995, used online and also translated into many different languages.

g. Fatigue

Clinically significant fatigue will be measured by the 9-item Fatigue Severity Scale (FSS) (Krupp, LaRocca, Muir-Nash, & Steinberg, 1989). The FSS has good internal consistency, stability, and sensitivity to change over time (Amato et al., 2001; Smedal et al., 2011). A mean score ≥ 4 has been suggested as a cut-off to indicate clinically significant fatigue and is widely used for people with MS (Lerdal, Celius, & Moum, 2003; Marrie et al., 2005; Smedal et al., 2011). A meaningful change on the FSS has been reported demonstrated to be a change of ≥ 1.9 points in people with MS (Learmonth et al., 2013) and so here a change in mean score of 1.9 points or more will be considered clinically meaningful.

h. Anxiety and depression

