The Hospital Anxiety and Depression Scale (HADS) for the presence of and severity of anxiety and depressive symptoms. The HADS is commonly used for screening for anxiety and depression, as well as selecting and monitoring treatment and has been used to measure depression in MS (Zigmond & Snaith, 1983).

i. Patient-reported disability

The Patient-Determined Disease Steps (PDDS) is a self-reported measure of ambulatory disability. The PDDS is scored ordinally from 0 (normal) to 8 (bed bound) with detailed descriptors and definitions. It correlates well with the EDSS and moderately with the widely used Multiple Sclerosis Functional Composite and has excellent test-retest reliability. PDDS is considered a practical tool to use to assess changes in disability over time (Hohol, Orav, & Weiner, 1999). One step will be considered a clinically meaningful change in the PDDS.

j. Self-efficacy

Self-efficacy (the belief in one's ability to produce the effects or outcomes one wants) will be measured using the University of Washington Self-Efficacy (UWSE) survey, a psychometrically sound instrument that includes 6 items for measuring self-efficacy, validated in MS (Amtmann et al., 2012).

Primary intervention quantitative outcomes/endpoints:

The two primary outcome measures for this study are changes (improvements) from baseline in 1. Physical Health Composite (PHC) and 2. Mental Health Composite (MHC) derived from the MSQOL-54 in the short-term and medium-term. Differences of at least five points have previously been determined as the minimum clinically meaningful change in an HRQOL measure (Osoba, Rodrigues, Myles, Zee, & Pater, 1998; Taphoorn & Bottomley, 2005). Previous data suggests a difference of five points is achievable in a sample of people with MS (Hadgkiss, Jelinek, Taylor, et al., 2015).

Secondary intervention quantitative outcomes/endpoints:

Secondary outcomes include clinically relevant changes (improvements) in depression, anxiety fatigue, disability and self-efficacy in the short-term and medium-term.

QUALITATIVE OUTCOMES

A qualitative study using semi-structured interviews will be conducted within one month and 12 months after completing the MS Online course (the same group of people with MS will be interviewed at both time points).

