9.3 STATISTICAL METHODS TO BE UNDERTAKEN

Quantitative data analysis:

Clinically significant fatigue will be defined as a mean FSS > 5 (Krupp et al., 1989). Anxiety and depression will be defined as higher HADS (Zigmond & Snaith, 1983). The UWSE will be assessed as a continuous term and dichotomised at the median as there is no established cut off point indicating sufficient self-efficacy.

Characteristics of quality of life (QoL) will be measured by the MSQOL-54, including physical and mental health composite scores and multiple subdomains. Linear regression will be used to determine cross-sectional and prospective relationships with QoL. Characteristics of disability will be assessed using linear regression. Characteristics of dichotomous clinically significant fatigue, depression and anxiety will be assessed by log-binomial regression. Characteristics of Self-efficacy composite scores will be assessed by linear and log-binomial regression for continuous and dichotomised self-efficacy, respectively. Characteristics of perceived social support scores will be

assessed by linear regression. All models will be assessed for potential confounders and appropriate adjustments will be made in analyses.

Qualitative data analysis:

Audio recordings will be transcribed for analysis and stored within Nvivo Software (www.qsrinternational.com) to enable data management. Data analysis will be conducted within a qualitative paradigm using reflexive thematic analysis (Braun 2014). Reflexive thematic analysis is considered the most appropriate analytic process due its lack of grounding in a particular philosophy (Braun 2006), and as a method suitable to exploring people's experiences, views and perceptions (Braun 2014) and its allowing expression of results in a way accessible to those in the wider community. Reflexive thematic analysis also emphasises the importance of the researcher being deeply involved in the research. Data will be analysed by the process of data familiarisation, coding, and theme development and refining. Data extracts (quotes) will illustrate themes.

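### Fatigue is a secondary outcome defined as clinically relevant improvement, but the plan analyses only whether FSS lies above 5; no analysis uses FSS change or the score.

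*Combined protocol and SAP*

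**What the plan says.** Section 5.3 defines the outcome in terms of improvement: "Secondary outcomes include clinically relevant changes (improvements) in depression, anxiety fatigue, disability and self-efficacy", in the short and medium term. Under the fatigue heading of the same section, the plan commits to a benchmark for the nine-item FSS: "a change in mean score of 1.9 points or more will be considered clinically meaningful". That paragraph also describes a mean score of 4 or more as a suggested and widely used cut-off in MS.

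Section 9.3 defines clinically significant fatigue as a mean FSS above 5, with a citation, and gives one model: "Characteristics of dichotomous clinically significant fatigue, depression and anxiety will be assessed by log-binomial regression". The statistical methods in the synopsis agree: "Characteristics of dichotomous clinically significant fatigue and depression will be assessed by log-binomial regression". Section 6.1 says only that fatigue and the other health outcomes will be compared between arms, and names no FSS measure or model.

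Other outcomes are handled differently. For quality of life: "Linear regression will be used to determine cross-sectional and prospective relationships with QoL". For disability: "Characteristics of disability will be assessed using linear regression". Self-efficacy is analysed both as a score and dichotomised. On covariates, section 9.3 says: "All models will be assessed for potential confounders and appropriate adjustments will be made in analyses". It does not name baseline FSS.

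**The concern.** The analysis answers a different question from the one the outcome poses. The outcome asks who improves, and by how much, against a 1.9-point benchmark. The analysis asks who is above a line at follow-up. The 1.9-point benchmark is never used.

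Section 5.3 gives a numerical meaningful change for three health outcomes: five points for HRQOL, 1.9 points for FSS and, for disability, "One step will be considered a clinically meaningful change in the PDDS". HRQOL and disability get linear regression, so their estimates are on the scale of their benchmarks. Fatigue is the only one of the three whose analysis cannot be read against its own benchmark, and no reason is given.

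The practical risk is that a modest real benefit on fatigue is missed, although the full score is collected at baseline and every follow-up. If the FSS measure and cut-off stay open, they could also be chosen after data are seen.

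**Working it through.** **Step 1: outcome against analysis, using the plan's own thresholds.** The plan gives no figure for fatigue to reproduce, so the first check is direct.

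| Change in mean FSS | Size | Meaningful under 5.3 (1.9 or more)? | Change in status under 9.3 (above 5)? |
|---|---|---|---|
| 5.1 to 4.9 | 0.2 | No | Yes |
| 5.0 to 3.0 | 2.0 | Yes | No |

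The two criteria can disagree in both directions.

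**Step 2: inputs for the size of the loss.** The documents give no FSS distribution, so these are assumptions: normal score; control mean 4.0, 4.5, 5.0 or 5.5; SD 1.4 or 1.7; baseline to follow-up correlation 0.6; true benefit 0.5 or 0.3 points; two-sided 5%. The number analysed uses the 42% loss at 12 months in section 9.1: 527 × 0.58 = 306 per arm.

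**Step 3: formulas.**

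- Status above 5, unadjusted: p0 and p1 are the normal probabilities of exceeding 5 in the control and intervention arms; z = |ln(p1/p0)| / sqrt[(1−p0)/(306·p0) + (1−p1)/(306·p1)].
- Score, unadjusted: z = benefit / (SD·sqrt(2/306)).
- Score adjusted for baseline: the previous z divided by sqrt(1−0.6²) = 0.8.
- Status adjusted for baseline status: simulation with 150,000 per arm, Poisson regression with robust standard errors standing in for log-binomial, rescaled to 306 per arm.

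**Step 4: one scenario in full** (mean 5.0, SD 1.4, benefit 0.5). p0 = 0.500 and p1 = 1 − Φ(0.5/1.4) = 0.360, so the risk ratio is 0.721 and its log is −0.327. The standard error is sqrt(0.00327 + 0.00580) = 0.0952, giving z = 3.44. For the score, z = 0.5/(1.4 × 0.0808) = 4.42, and with baseline adjustment 4.42/0.8 = 5.52.

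**Step 5: range over all eight scenarios.**

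| Analysis | Benefit 0.5: z | Power | Benefit 0.3: z | Power |
|---|---|---|---|---|
| Status above 5 | 2.58–3.44 | 73–93% | 1.59–2.10 | 36–55% |
| Status, adjusted for baseline status | 2.79–3.79 | 80–97% | 1.70–2.33 | 40–65% |
| Score | 3.64–4.42 | 95–99% | 2.18–2.65 | 59–76% |
| Score, adjusted for baseline | 4.55–5.52 | over 99% | 2.73–3.31 | 78–91% |

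**Step 6: efficiency.** The squared ratio of z values is the fraction of participants on which the better analysis would reach the same precision. It does not depend on the number analysed.

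- Status against score, both unadjusted (no correlation needed): 0.45 to 0.63.
- Both adjusted for baseline: 0.33 to 0.49 at correlation 0.6, and 0.23 to 0.35 at 0.8.
- Both adjusted, with the score bounded at 1 and 7 in steps of 1/9 (assumed) and correlation 0.6: 0.32 to 0.52.

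**Step 7: the cut-off.** Scores from 4.0 to 5.0 inclusive count as significant fatigue at 4 or more but not at above 5. For a 0.5-point benefit the control prevalence is 0.50 to 0.86 at 4 or more and 0.24 to 0.64 at above 5, and the risk ratio is 0.72 to 0.89 and 0.60 to 0.81 respectively. The risk difference is 0.089 to 0.140 at both, and z differs by at most 0.48 within any scenario. The choice changes the reported risk ratio much more than the conclusion.

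**The case against.** The strongest objection is that the mismatch and the power loss concern different endpoints. The analysis that literally matches section 5.3 is the proportion improving by at least 1.9 points. On the same assumptions its power at 306 per arm is about 72% to 80% for a 0.5-point benefit, depending on the test, and about 32% to 37% for 0.3, which is no better than status. That is correct. The power gain comes from the baseline-adjusted score, so the proportion improving should be supportive and the score should lead. The score is still on the scale of the 1.9-point benchmark, which status is not.

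Second, benefits of 0.3 and 0.5 are only 16% and 26% of 1.9 points. However, 1.9 is stated as a change in a person's score, and a mean difference between arms need not reach it for more people to improve by that much. Reporting the estimate with its confidence interval and the proportion improving would show a small effect as small.

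Third, 306 per arm is one reading. Section 9.1 also describes 527 per arm as having follow-up data and calls the 42% loss a likely overestimate. At 527 analysed, unadjusted status has 92% to 99% power for a 0.5-point benefit and 55% to 79% for 0.3. This weakens the power argument for the larger benefit but leaves the efficiency ratios unchanged.

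Fourth, depression and anxiety are also analysed only as status, and the disability model names neither change nor a one-step improvement. Both are true, so the gap is wider than fatigue. Section 5.3 gives no numerical change benchmark for depression or anxiety, which is why fatigue is the clearest case.

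Fifth, section 5.3 reports the cut-off of 4 without adopting it, so above 5 is the only operative rule. That stands, and the cut-off by itself is a clarification.

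Finally, the Data Analysis section leaves a statistical analysis plan to be developed. That is the place for the correction, but the documents already state a method for fatigue, and it is the weaker one.

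**Conclusion.** The concern holds. Fatigue is defined as clinically relevant improvement with a 1.9-point benchmark, and the only stated analysis is of status above 5. Even with baseline status in the model, that analysis has the precision of a baseline-adjusted score analysis on about 33% to 49% of the participants. These figures rest on an assumed normal score and a correlation of 0.6, because the documents give no FSS distribution; the mismatch between outcome and analysis rests on the text alone. The missing explanation for the cut-off is a lesser matter. This should be corrected, but it concerns a secondary outcome: the primary PHC and MHC analysis and the sample size are not affected.

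**What to change.** In section 9.3 and the analysis plan still to be written:

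- Compare mean FSS between arms at each follow-up by linear regression adjusted for baseline FSS, and state that this analysis carries the fatigue conclusion.
- Report the estimate with its confidence interval and interpret it alongside the 1.9-point benchmark. Give the proportion improving by at least 1.9 points as supportive, with its denominator stated, because participants with low baseline scores have little room to fall by that much.
- Keep the log-binomial analysis of status as supportive, adjusted for baseline status.
- Reconcile sections 5.3 and 9.3 to one justified cut-off with its inequality sign, and report the other as a sensitivity analysis.

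The cost is edits to sections 5.3 and 9.3, a matching line in the synopsis, and a few extra secondary analyses. FSS is already scheduled at baseline, 6 months, 12 months and 2.5 years (Table 1), so no new data are needed. The downside is more fatigue results to report, which is why one must be named in advance as decisive.

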Primary Objectives:	
To determine whether participants adhering to lifestyle modification recommendations outlined in the MS Online intervention course have clinically significant increased health-related quality of life (HRQOL) in both domains of physical and mental health compared with participants following recommendations of the MS Online standard-care course. These outcomes will be examined in the short-term (6 and 12 months) and in the medium-term (2.5 years).
 
That is, we aim to determine whether participants in the Online intervention course following recommended lifestyle modifications have clinically significant and material increases in Physical Health Composite (PHC) and Mental Health Composite (MHC) scores, as derived from the validated tool designed to measure HRQOL in people with MS (MSQOL-54) compared with participants following recommendations of the Online standard-care course.

Secondary Objectives	
To determine whether participants following the lifestyle modification recommendations in the Online MS intervention course have improved depression, anxiety, fatigue, disability and self-efficacy in the short-term and medium-term compared with people following recommendations of the Online MS standard-care course.

Inclusion Criteria:	
Eligible participants must:
 
 1. Be able to read, write, and speak English; 2. Be 18 years old or over; 3. Have a confirmed diagnosis of relapsing-remitting MS by a neurologist preceding recruitment; 4. Be able to access the internet and be able to view sessions.
Exclusion Criteria:	
Exclusion criteria of participants include:
 
 1. Experiencing any serious co-morbid chronic illness or neurological illness/injury other than MS that would threaten regular participation or significantly affect the outcome measures in its own right, such as motor neurone disease or stroke, as determined by the study investigators; 2. Currently participating in another study or self-management program involving modification of lifestyle.
Number of Planned Participants:	
1054 participants, 527 in each arm at 1:1 allocation (intervention and standard-care arm)

Investigational product:	
Not applicable

Safety considerations:	
Participation in the study poses no physical risk to participants as the proposed RCT involves taking part in an Online MS

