Observational studies have found physical activity is associated with increased energy and social functioning and improved physical and mental health outcomes.(Marck et al., 2014; Marck, Learmonth, Chen, & van der Mei, 2020; Motl & Gosney, 2008)

Key questions:

Does participation of people with MS in the MS Online intervention course change lifestyle behaviours compared with participants in an MS Online standard care course in the:

- 1) Short-term
- 2) Medium-term

What is the effect on participant health outcomes from different levels of adoption and adherence to lifestyle recommendations in the MS Online intervention course compared with MS Online standard-care course with respect to:

- 1) Quality of life

- 2) Fatigue
- 3) Depression
- 4) Anxiety
- 5) Disability
- 6) Self-efficacy

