5.2 STUDY AIMS

To quantitatively and qualitatively assess the arms of the Multiple Sclerosis Online Course in an RCT (the MS Online intervention course and MS Online standard-care course). We aim to measure:

- 1) The degree of engagement with and participation in the course
- 2) Adoption of lifestyle behaviours change following course completion
- 3) Adherence to lifestyle behaviour change over time
- 4) Short-term and medium-term health outcomes and
- 5) To compare all these outcomes between both arms.

Overall, the proposed RCT will enable a causal relationship between lifestyle factors and clinical and health outcomes to be examined.

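### The comparison of randomised arms for PHC and MHC has no fixed model: the baseline score is collected before randomisation but is not a stated covariate, and covariates are left to a confounder assessment

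*Combined protocol and SAP*

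**What the plan says.** For quality of life, Section 9.3 states: "Linear regression will be used to determine cross-sectional and prospective relationships with QoL". It closes the quantitative part with "All models will be assessed for potential confounders and appropriate adjustments will be made in analyses". The Statistical Methods row of the synopsis has a near-identical rule: "All models will be assessed for potential clinical and demographic confounders and appropriate adjustments will be made in analyses". Neither place names an arm term, the baseline PHC or MHC score, a covariate list or a selection rule.

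The comparison of arms is nevertheless an aim. Section 5.2 ends its list with "To compare all these outcomes between both arms", Section 5.1 states a superiority hypothesis between arms, and Section 9.1 sizes the trial for a 5-point difference between arms. Sections 5.3 and 9.1 define the two primary outcomes as changes in PHC and MHC.

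Other parts frame the question by adherence. The primary objective in the synopsis opens "To determine whether participants adhering to lifestyle modification recommendations outlined in the MS Online intervention course", and a key question in Section 4.2 is "What is the effect on participant health outcomes from different levels of adoption and adherence to lifestyle recommendations". Section 6.1 item IX bases its 12-month decision on adhering participants.

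Table 1 schedules the MSQOL-54 at baseline. Sections 6.3 and 7.1 place completion of the baseline questionnaire before randomisation, which is simple and 1:1.

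**The concern.** One covariate rule covers two different kinds of analysis. When arms are compared as randomised, baseline differences arise by chance. A search for confounders then becomes a data-dependent choice of covariates for the primary estimate. In the adherence-based and lifestyle-outcome analyses, randomisation gives no protection and confounder assessment is the right tool. The text does not separate the two.

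Two things are at stake. The first is prespecification of the primary estimate. The second is precision: as written, baseline need enter only by subtraction, in the change score. In large samples a linear model with the baseline score as covariate is at least as precise as either the change score or the follow-up score. It also corrects chance imbalance in the baseline score, which simple randomisation does nothing to limit.

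**Working it through.** **Inputs from the documents.** Difference 5 points, power 80%, 527 per arm, 42% loss by 12 months (Section 9.1); Bonferroni over PHC and MHC (Section 9.2).

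**Inputs not in the documents, so assumed.** SD; correlation rho between baseline and follow-up score (range 0.3 to 0.7); two-sided alpha 0.05/2 = 0.025 per outcome.

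**The plan's own figure.** It cannot be rebuilt from stated inputs alone, because the SD and numeric alpha are missing. With SD 20:

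- n per arm = 2 × (20/5)² × (2.2414 + 0.8416)² = 32 × 9.505 = 304.2, so 305.
- Allowing for loss: 305/0.58 = 525.9, so 526 against 527 stated.

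This solution is not unique. SD 22 with alpha 0.05 gives 304, then 525. If all 527 per arm have follow-up data, the implied SD is 26.3. SD 20 is therefore a back-solved working value. With it, 527 × 0.58 = 306 per arm are analysed.

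**Effective SD, equal SDs at both times.**

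- Follow-up score: SD
- Change score: SD × √(2(1 − rho))
- Baseline-adjusted: SD × √(1 − rho²)

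The adjusted variance is thus (1 + rho)/2 of the change-score variance and (1 − rho²) of the follow-up-score variance.

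**Power** = Φ(5/(effective SD × √(2/n)) − 2.2414). Worked at rho 0.5, n = 306:

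- Follow-up or change score: standard error 20 × √(2/306) = 1.617; 5/1.617 − 2.241 = 0.851; power 80.3%.
- Adjusted: effective SD 17.32, standard error 1.400; 5/1.400 − 2.241 = 1.330; power 90.8%.

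| rho | Power: follow-up / change / adjusted | n per arm for 80% power |
|---|---|---|
| 0.3 | 80.3 / 64.5 / 84.1% | 305 / 426 / 277 |
| 0.5 | 80.3 / 80.3 / 90.8% | 305 / 305 / 229 |
| 0.6 | 80.3 / 88.8 / 94.8% | 305 / 244 / 195 |
| 0.7 | 80.3 / 96.0 / 98.2% | 305 / 183 / 156 |

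The reading with 527 analysed and SD 26.3 gives the same pattern (change/adjusted 64/84% at rho 0.3, 96/98% at 0.7).

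**Unequal SDs.** If the follow-up SD is k times the baseline SD, the variance ratio of adjusted to change score is k²(1 − rho²)/(1 + k² − 2·rho·k). As k runs from 0.9 to 1.2, the saving falls from 42% to 24% at rho 0.3, from 33% to 13% at 0.5, from 29% to 8% at 0.6 and from 25% to 3% at 0.7. Against the follow-up score it stays at rho².

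**The only hint at an SD.** Section 5.3 links five points to half a standard deviation, which would imply SD 10. That gives 2 × (10/5)² × 9.505 = 76.04, so 77 per arm, and 77/0.58 = 133 with loss, which does not reproduce 527. At SD 10 and 306 per arm, power is at least 99.8% for all three analyses. Only the interval narrows: at rho 0.5 the 97.5% half-width falls from 1.81 to 1.57 points.

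**The case against.** The strongest reply is that this is unfinished specification, not a wrong method. The Data Analysis section assigns development of a statistical analysis plan to the data management team. Section 6.3 blinds those who perform the analyses, which limits choosing covariates to favour an arm. The wording is also broad enough to admit a baseline score. All of this is true. But a listed task does not fix the model, blinding does not prespecify covariates or recover precision, and permission is not commitment.

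A second reply is that the gain rests on undocumented inputs and can be small. That also stands. Against a change score with rho 0.7, power moves only from 96% to 98%, and at SD 10 it does not move materially.

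A third is that a fixed arm model does not serve a primary objective worded around adhering participants. This is correct, and it means the population for the primary comparison has to be settled together with the model.

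Some stronger readings are tempting. A reader might infer that the plan excludes baseline adjustment, that the trial is underpowered, or that its result will be biased. The documents support none of these: adjustment is allowed, and 527 per arm is compatible with several SD and alpha combinations. A reader might also infer that baseline adjustment deals with the missing data. It does not. Powered on 306 of 527 per arm, it is a complete-case analysis that needs missingness to be explained by arm and baseline score.

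Nor can one say that a repeated-measures model would add little, because that depends on correlations between visits that the documents do not give. As an illustration, assume SD 20.05, 79% with a 6-month score and a 6-to-12-month correlation of 0.8. Power then rises from 90.6% to 94.6% at rho 0.5, and from 83.9% to 90.1% at rho 0.3.

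**Conclusion.** The point holds as a recommended change. The current text does not fix a baseline-adjusted model for the comparison of arms on PHC and MHC, and it applies a confounder search where randomisation makes one unnecessary. The direction of the precision gain is secure in large samples: adjustment is never less precise than the change score or the follow-up score. Its size is not secure. Under SD 20, equal SDs, two-sided alpha 0.025 and 306 per arm, power is 84 to 98% adjusted, against 65 to 96% for the change score and 80% for the follow-up score, over rho 0.3 to 0.7. The gain over a change score is small when rho is high or the follow-up SD is larger than at baseline. If the SD were near 10, only interval width would improve. The benefit of fixing covariates in advance does not depend on these assumptions. Nothing here shows that the sample size is wrong.

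**What to change.** Before any follow-up outcome data are examined by arm, amend Section 9.3 and the synopsis, and carry the text into the statistical analysis plan:

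1. State that the comparison of arms as randomised for PHC, and separately for MHC, is a linear model with arm and the baseline value of that score.
2. Name any further covariates in advance, from baseline data only.
3. Restrict the confounder assessment to the adherence-based and lifestyle-outcome analyses, and say so.
4. Reconcile the adherence wording of the synopsis objective with the between-arm comparison in Sections 5.1, 5.2 and 9.1, so that the as-randomised comparison is the one called primary.
5. Reconcile the primary time points: the synopsis objective gives 6 and 12 months and 2.5 years, Section 6.1 item IX gives 12 months and 2.5 years.
6. State the missing-data assumption behind the baseline-adjusted model, and add a sensitivity analysis in view of the 42% expected loss.

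The cost is wording and minor analysis work. No new data, visits or participants are needed.
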